6.2.3 Vaccine Administration

Each vaccination will consist of three total intra-dermal injections, one each in the right and left anterior upper thighs, and one in the non-dominant upper arm (unless

contraindicated). In the event that the specified limb is contraindicated, the dominant arm may be used. Vaccine injection sites shall be at least 5 cm at needle entry from the nearest neighbor. The approximate volume of each vaccination injection is approximately 0.7 – 0.8 mL

Application of a lidocaine based topical anesthetic (may include but is not limited to EMLA or ELA-MAX) cream at each injection site approximately 1-2 hours prior to vaccination will be recommended to diminish the discomfort associated with the intra-dermal injections. The topical anesthetic is optional and participants are allowed to decline its use. Self-application of the topical anesthetic is allowed after the research participant receives instruction. If the research participant does not comply with application instructions, the topical anesthetic may be applied by the research nurse. If the subject is allergic to lidocaine, the topical anesthetic will not be used. All research participants will be seen in the oncology outpatient center for vaccine administration and monitoring for at least 30 minutes after vaccination is completed. Those administrating the vaccine will record:

- a. Clinical lot number. Record of this will be kept by CTL in order to maintain blinding
- b. Date of vaccine administration
- c. Number of syringes dispensed
- d. Total vaccine dose. Record of this will be kept by CTL in order to maintain blinding
- e. Vaccination sites

Vaccinations will occur on Day 14 (± 3 days) of cycles 1, 2, 3 and 6 and then annually from enrollment thereafter through 36 months.

Treatment will be discontinued if any of the following occur:

- a. Intercurrent illness that prevents further administration of treatment,
- b. Unacceptable adverse events(s),
- c. The patient decides to withdraw from the study, or
- d. General or specific changes in a patient's condition render further treatment inappropriate in the clinical judgment of the investigator.

6.2.4 Potential Vaccine Toxicities

Toxicities associated with the intravenous administration of Pentaspan® include circulatory overload, abnormalities of coagulation (prolonged prothrombin, partial thromboplastin and clotting times), and hypersensitivity reactions characterized by wheezing, urticaria, hypotension, and anaphylactic/anaphylactoid reactions. Additionally, patients who are allergic to corn can also develop hypersensitivity to Pentaspan®.

The experience with K562/GM-CSF to date has shown it to be safe and well tolerated ⁴⁸. Elevated levels of GM-CSF can be detected in the serum for 3-5 days post vaccination, and this is accompanied by a transient rise in the white blood cell, neutrophil, and absolute

eosinophil counts. Toxicity is generally limited to myalgias and grade 1-2 injection site erythema, induration, tenderness, and localized pruritus. Most patients experience local vaccine site reactions that last for approximately 1 week; induration has ranged from 0.5 cm to as great as 20 cm. In other trials of GM-CSF producing vaccines, systemic reactions have included fever, headache, rash, generalized pruritus, and malaise.

As with any vaccine, there is a possibility of a serious allergic reaction although to date this has not been observed with any of the GM-CSF based vaccines administered here at Johns Hopkins. As with any investigational drug, other adverse reactions may develop that have not yet been described.

There is a theoretical risk of autoimmune disease reactivation or development with GM-CSF producing vaccines. In a previous multiple myeloma vaccine trial, induction of immune responses to autologous tumor cells has been demonstrated in vitro. Importantly, all multiple myeloma patients who had undergone autologous stem-cell transplant followed by vaccination have had normal kinetics of engraftment. There has been no serological or clinical evidence of autoimmune disease to date arising in recipients of the K562/GM-CSF vaccine in the previous AML, CML and myelomatrials.

6.2.5 Availability

The vaccine is derived from the three master banks for K562/GM-CSF, H929 and U266. The master cell banks are the source material for all working clinical lots. The clinical grade allogeneic myeloma K562/GM-CSF vaccine will be manufactured by the GMP facilities operated by Aduro Biotech, and shipped to Johns Hopkins.

6.3 PREVNAR-13®

Other names: Pneumococcal 13-Valent Conjugate Vaccine

Classification: Infectious vaccine

Supplier: Prevnar-13 will be purchased from Wyeth Pharmaceuticals.

Dosage:

Prevnar-13 will be administered at 0.5ml dose by intramuscular injection. This dose will thus contain serotypes 1, 3, 4, 5, 6A, 6B, 7F, 9V, 14, 18C, 19A, 19F, and 23F and approximately 20 μ g of CRM₁₉₇ carrier protein; and 0.125mg of aluminum phosphate.

Since the product is a suspension containing an adjuvant, shake vigorously immediately prior to use to obtain a uniform suspension in the vaccine container. The vaccine should not be used if it cannot be resuspended or if particulate matter or discoloration is found.

Storage:

Vaccine is to be stored refrigerated at 2°C to 8°C (36°F to 46°F). It should not be frozen.

Contraindications:

Hypersensitivity to any component of the vaccine, including diphtheria toxoid, is a contraindication to use of this vaccine.

Warnings:

Healthcare professionals should prescribe and/or administer this product with caution to patients with a possible history of latex sensitivity since the packaging contains dry natural rubber.

Precautions:

Prevnar® is for intramuscular use only. Prevnar SHOULD UNDER NO CIRCUMSTANCES BE ADMINISTERED INTRAVENOUSLY. The safety and immunogenicity for other routes of administration (e.g., subcutaneous) have not been evaluated.

64 LENALIDOMIDE:

[figure not shown]
6.4.1 Other names: Revlimid®

6.4.2 Classification: Immunomodulatory drug

6.4.3 Description:

Revlimid® (lenalidomide), a thalidomide analogue, is an immunomodulatory agent with anti-angiogenic properties. The chemical name is 3-(4-amino-1-oxo 1,3-dihydro -2H-isoindol-2-yl) piperidine-2,6-dione and it has the following chemical structure:

Chemical Structure of Lenalidomide:

3-(4-amino-1-oxo 1,3-dihydro-2H-isoindol-2-yl) piperidine-2,6-dione

The empirical formula for lenalidomide is C₁₃H₁₃N₃O₃, and the gram molecular weight is 259.3.

Lenalidomide is an off-white to pale-yellow solid powder. It is soluble in organic solvent/water mixtures, and buffered aqueous solvents. Lenalidomide is more soluble in organic solvents and low pH solutions. Solubility was significantly lower in less acidic buffers, ranging from about 0.4 to 0.5 mg/ml. Lenalidomide has an asymmetric carbon

atom and can exist as the optically active forms S(-) and R(+), and is produced as a racemic mixture with a net optical rotation of zero.

6.4.4 Mode of action:

The mechanism of action of lenalidomide remains to be fully characterized. Lenalidomide possesses immunomodulatory and antiangiogenic properties. Lenalidomide inhibited the secretion of pro-inflammatory cytokines and increased the secretion of anti-inflammatory cytokines from peripheral blood mononuclear cells. Lenalidomide inhibited cell proliferation with varying effectiveness (IC50s) in some but not all cell lines. Of cell lines tested, lenalidomide was effective in inhibiting growth of Namalwa cells ⁴⁹ (a human B cell lymphoma cell line with a deletion of one chromosome 5) but was much less effective in inhibiting growth of KG-1 cells (human myeloblastic cell line, also with a deletion of one chromosome 5) and other cell lines without chromosome 5 deletions. Lenalidomide inhibited the expression of cyclooxygenase-2 (COX-2) but not COX-1 invitro.

Lenalidomide is a proprietary IMiD™ compound of Celgene Corporation. IMiD™ compounds have both immunomodulatory and anti-angiogenic properties which could confer antitumor and antimetastatic effects. ⁵⁰ Lenalidomide has been demonstrated to possess anti-angiogenic activity through inhibition of bFGF, VEGF and TNF-alpha induced endothelial cell migration, due at least in part to inhibition of Akt phosphorylation response to bFGF. In addition, lenalidomide has a variety of immunomodulatory effects. Lenalidomide stimulates T cell proliferation and the production of IL-2, IL-10 and IFN-gamma, inhibits IL-1 beta and IL-6 and modulates IL-12 production. Upregulation of T cell derived IL-2 production is achieved at least in part through increased AP-1 activity.

Although the exact antitumor mechanism of action of lenalidomide is unknown, a number of mechanisms are postulated to be responsible for lenalidomide's activity against multiple myeloma. Lenalidomide has been shown to increase T cell proliferation, which leads to an increase in IL-2 and IFN-gamma secretion. The increased level of these circulating cytokines augment natural killer cell number and function, and enhance natural killer cell activity to yield an increase in multiple myeloma cell lysis. In addition, lenalidomide has direct activity against multiple myeloma and induces apoptosis or G1growth arrest in multiple myeloma cell lines and in multiple myeloma cells of patients resistant to melphalan, doxorubicin anddexamethasone.

6.4.5 Adverse effects:

The most frequently reported adverse events reported during clinical studies with lenalidomide in oncologic and non-oncologic indications, regardless of presumed relationship to study medication, include: anemia, neutropenia, thrombocytopenia and pancytopenia, abdominal pain, nausea, vomiting and diarrhea, dehydration, rash, itching, infections, sepsis, pneumonia, UTI, Upper respiratory infection, cellulites, atrial fibrillation, congestive heart failure, myocardial infarction, chest pain, weakness, hypotension, hypercalcemia, hyperglycemia, back pain, bone pain, generalized pain, dizziness, mental

status changes, syncope, renal failure, dyspnea, pleural effusion, pulmonary embolism, deep vein thrombosis, CVA, convulsions, dizziness, spinal cord compression, syncope, disease progression, all cause death and fractures. Complete and updated adverse events are available in the FDA label.

6.4.6 Storage:

Lenalidomide should be stored at room temperature away from direct sunlight and protected from excessive heat and cold.

6.4.7 Prescribing Lenalidomide:

Lenalidomide (Revlimid®) will be supplied commercially to research subjects for the duration of their participation in this trial by their insurance providers. Lenalidomide will be provided in accordance with Celgene Corporation's Revlimid REMS® program. Per standard Revlimid REMS® program requirements, all physicians who prescribe lenalidomide for research subjects enrolled into this trial, and all research subjects enrolled into this trial, must be registered in, and must comply with, all requirements of the Revlimid REMS® program. Prescriptions must be filled within 7 days. Only enough lenalidomide for one cycle of therapy will be supplied to the patient during each cycle.

Further information about the Revlimid REMS® program is available at www.celgeneriskmanagement.com.

6.4.8 Pharmacokinetics and Drug Metabolism:

6.4.8.1 Absorption:

Lenalidomide, in healthy volunteers, is rapidly absorbed following oral administration with maximum plasma concentrations (C_{max}) occurring between 0.625 and 1.5 hours post-dose. Co-administration with food does not alter the extent of absorption ⁵¹, but does reduce the C_{max} by 36%. The pharmacokinetic disposition of lenalidomide is linear, i.e. C_{max} and AUC increase proportionately with increases in dose. Multiple dosing at the recommended dose-regimen does not result in drug accumulation.

Pharmacokinetic analyses were performed on 15 multiple myeloma patients treated in the phase I studies. Absorption was found to be rapid on both Day 1 and Day 28 with time to maximum blood levels ranging from 0.7 to 2.0 hours at all dose levels (5mg, 10mg, 25mg, and 50mg). No plasma accumulation was observed with multiple daily dosing. Plasma lenalidomide declined in a monophasic manner with elimination half-life ranging from 2.8 to 6.1 hours on both Day 1 and 28 at all 4 doses. Peak and overall plasma concentrations were dose proportional over the dosing range of 5mg to 50mg.⁵¹ Exposure in multiple myeloma patients is 57% higher than in healthy male volunteers.

6.4.8.2 Pharmacokinetic Parameters:

Distribution:

In vitro (¹⁴C)-lenalidomide binding to plasma proteins is approximately 30%.

Metabolism and Excretion:

The metabolic profile of lenalidomide in humans has not been studied. In healthy volunteers, approximately two-thirds of lenalidomide is eliminated unchanged through urinary excretion. The process exceeds the glomerular filtration rate and therefore is partially or entirely active. Half-life of elimination is approximately 3 hours.

6.4.9 Supplier(s)

Celgene Corporation will supply Revlimid® (lenalidomide) commercially to study participants.

6.4.10 Packaging

Lenalidomide will be shipped directly to patients. Each bottle will contain a sufficient number of capsules for one cycle of dosing.

6.4.11 Dosage forms:

5, 10, 15 and 25 mg capsules.

6.4.12 Dosing regimen and dose reductions:

Patients will need to be on a maintenance dose of lenalidomide upon being enrolled in the study. Doses of lenalidomide for investigation can vary from 5-25 mg/day, orally on days 1 - 21 followed by 7 days rest (28 day cycle). Patients may be kept on whichever regimen of Revlimid they were taking at the time of enrollment, or changed to an adjusted dose at the PI's discretion.

Prescriptions must be filled within 7 days.

If a patient is on a 10mg dose of lenalidomide upon enrollment into the study, they can be dose reduced to 5mg and remain on study. If a patient requires a dose reduction to less than 5mg, further continuation on study must be approved by the principal investigator.

If a dose of lenalidomide is missed, it should be taken as soon as possible on the same day. If it is missed for the entire day, it should not be made up.

Patients who take more than the prescribed dose of lenalidomide should be instructed to seek emergency medical care if needed and contact study staff immediately.

6.4.13 Dose adjustments/modifications can be made if needed based on toxicity:**Table 1: LENALIDOMIDE Dose Reduction Steps**

Starting Dose	Dose Reduction
15 mg daily on Days 1-21 every 28 days	10 mg daily on Days 1-21 every 28 days
10 mg daily on Days 1-21 every 28 days	5 mg daily on Days 1-21 every 28 days

Overdose

Overdose, as defined for this protocol, refers to Revlimid® dosing only.

On a per dose basis, an overdose is defined as the following amount over the protocol-specified dose of Revlimid® assigned to a given patient, regardless of any associated adverse events or sequelae.

PO any amount over the protocol-specified dose

IV 10% over the protocol-specified dose

SC 10% over the protocol-specified dose

On a schedule or frequency basis, an overdose is defined as anything more frequent than the protocol required schedule or frequency.

On an infusion rate basis, an overdose is defined as any rate faster than the protocol-specified rate. Complete data about drug administration, including any overdose, regardless of whether the overdose was accidental or intentional, should be reported in the case report form.

6.4.14 Concomitant therapy:

Subjects should receive full supportive care, including transfusions of blood and blood products, antibiotics, and antiemetics when appropriate. Considering that all patients will be on lenalidomide for several cycles prior to enrolling on the study, they will be kept on whichever regimen they were taking at the time of enrollment.

6.4.15 Prohibited Concomitant Therapy

Concomitant use of other anti-cancer therapies, corticosteroids, G-CSF, including radiation, thalidomide, or other investigational agents is not permitted while subjects are receiving protocol therapy during the treatment phase of the study. Topical, ophthalmic and inhaled corticosteroids are excluded.

6.4.16 Anticoagulation Considerations

Lenalidomide increases the risk of thrombotic events in patients who are at high risk or with a history a thrombosis particularly when combined with steroids (e.g. dexamthasone, prednisone), or other anticancer drugs known to cause thrombosis (e.g. anthracyclines [Doxil, Adriamycin] and erythropoietin).

Consideration should be given to use of aspirin (81 or 325 mg) or some other form of prophylactic anticoagulant as deemed appropriate. Low molecular weight heparin may be utilized in patients that are intolerant to ASA. Coumadin should be used with caution and close monitoring of INR. If prophylaxis is used, it should be held when platelet counts < 50,000, and then restarted when platelet counts are above this level.

6.4.17 General Concomitant Medication and Supportive Care Guidelines

Because there is a potential for interaction of lenalidomide with other concomitantly administered drugs, the case report form must capture the concurrent use of all other drugs, over-the-counter medications, or alternative therapies.

The allogeneic myeloma K562/GM-CSF vaccine is an immune based treatment. As such, immunosuppressants in the form of steroids, cyclosporine, imuran, cellcept, sirolimus, tacrolimus and others should not be administered during this clinical trial. For questions, address the Primary Investigator.

65 Duration of Follow-up

Patients will be followed for a minimum of 36 months after enrollment in the study or until relapse or death, whichever occurs first. Patients removed from study treatment for unacceptable adverse events will be followed until resolution or stabilization of the adverse event.

66 Dose delay/Dose modifications

There are no dose modifications for the vaccine. Lenalidomide dose adjustments as noted in section **6.4.13**.

NCI CTC Toxicity Grade (CTC AE 4.0)	Dose Modification Instructions
Grade 3 neutropenia associated with fever (temperature $\geq 38.5^{\circ}\text{C}$) or Grade 4 neutropenia	
 Hold (interrupt) lenalidomide dose. Follow CBC weekly. If neutropenia has resolved to \leq grade 2, restart lenalidomide at next lower dose level and continue through the scheduled end of the cycle. Otherwise, omit for remainder of cycle and reduce the dose of lenalidomide by 1 dose level at the start of the next cycle. Omitted doses are not made up.
Thrombocytopenia \geqGrade 3 (platelet count $< 50,000/\text{mm}^3$)	
 Hold (interrupt) lenalidomide dose. Follow CBC weekly. NOTE: Consider criteria (perhaps based on platelet count) for holding and then resuming prophylactic anti-coagulation, if applicable. If thrombocytopenia resolves to \leq grade 2, restart lenalidomide at next lower dose level and continue through scheduled end of the cycle. Otherwise, omit for remainder of cycle and reduce the dose of lenalidomide by 1 dose level at start of next cycle. Omitted doses are not made up.
Non-blistering rash	
Grade 3	
 If Grade 3, hold (interrupt) lenalidomide dose. Follow weekly. If the toxicity resolves to \leq grade 1, restart lenalidomide at next lower dose level and continue through the scheduled end of the cycle. Otherwise, omit for remainder of cycle and reduce the dose of lenalidomide by 1 dose level at the start of the next cycle. Omitted doses are not made up.
Grade 4	
 If Grade 4, discontinue lenalidomide. Remove patient from study.
Desquamating (blistering) rash- any Grade	
 Discontinue lenalidomide. Remove patient from study.
Neuropathy	
Grade 3	
 If Grade 3, hold (interrupt) lenalidomide dose. Follow at least weekly. If the toxicity resolves to \leq grade 1 prior to Day 21, restart lenalidomide at next lower dose level and continue through the scheduled end of the cycle. Otherwise, omit for remainder of cycle and reduce the dose of lenalidomide by 1 dose level at the start of the next cycle. Omitted doses are not made up.
Grade 4	
 If Grade 4, discontinue lenalidomide. Remove patient from study.
Venous thrombosis/embolism \geq Grade 3	
 Hold (interrupt) lenalidomide and start anticoagulation; restart lenalidomide at investigator's discretion (maintain dose level). Omit lenalidomide for remainder of cycle. See Anticoagulation Consideration (Section 5.6.1.2)
Hyperthyroidism or hypothyroidism	
 Omit lenalidomide for remainder of cycle, evaluate etiology, and initiate appropriate therapy. See Instructions for Initiation of a New Cycle and reduce the dose of lenalidomide by 1 dose level.
other non-hematologic toxicity \geq Grade 3	
 Hold (interrupt) lenalidomide dose. Follow at least weekly. If the toxicity resolves to \leq grade 2 prior to Day 21, restart lenalidomide and continue through the scheduled end of the cycle. Otherwise, omit for remainder of cycle. Omitted doses are not made up. For toxicity attributed to lenalidomide, reduce the lenalidomide dose by 1 dose level when restarting lenalidomide.

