This is a single institution, three- arm, randomized controlled, Phase II study examining the clinical efficacy of an allogeneic GM-CSF secreting myeloma vaccine in combination with lenalidomide (with or without Prevnar) compared to lenalidomide and placebo (control arm). Patients enrolled in the study must have two disease measurements (including the last one) consistent with a near complete remission (M-spike negative with persistence of immunofixation), or complete remission (M-spike negative, negative immunofixation, and <5% clonal plasma cells on bone marrow) per criteria for response in a 3 month period. All patients must be minimal residual disease (MRD) positive at 10^{-4} by NGS sequencing at enrollment. Prior to enrollment, patients will have been treated with a lenalidomide containing regimen for a minimum of 6 cycles. All patients will continue on a standard dose of lenalidomide as a single agent until progression, or treatment limiting toxicity, following enrollment. Patients will be randomized to receive either an allogeneic myeloma vaccine and Prevnar vaccine in combination with lenalidomide, or allogeneic myeloma vaccine without Prevnar vaccine in combination with lenalidomide, or lenalidomide in combination with placebo. Patients will receive allogeneic myeloma vaccine or placebo injections on day 14 (+/-3 days) of cycles 1, 2, 3 and 6 from enrollment, and then annually thereafter for up to 3 years. If assigned to allogeneic myeloma vaccine plus Prevnar vaccine arm, Prevnar-13 will be administered with each allogeneic myeloma vaccine. If assigned to either of the two arms that do not include Prevnar, then patients will receive a placebo in lieu of Prevnar on the same schedule. All patients will be followed for a minimum of 3 years.

STUDY DURATION: 3-5 years**TOTAL SAMPLE SIZE:** 54 (18 per arm)

DOSING REGIMEN(S):	STUDY DRUG SUPPLIES:

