7.4 Follow-Up

Subjects who discontinue study treatment for any reason will undergo a safety assessment approximately 30 days post the last dose of study drug.

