11 BIOSTATISTICAL ANALYSIS

11.1 Sample Size Considerations

The primary endpoint of this phase II study is progression free survival (PFS). The primary analysis will compare the control arm (lenalidomide plus placebo) versus the pooled allogenic myeloma vaccine arms (with and without Prevnar). In a prior study, the median PFS for patients on Len containing therapy was 17.9 months. Patients will be accrued over the course of 2 years with a minimum follow-up of 3 years (i.e. all patients will have 3-5 years of follow-up). A sample size of 54 patients (18 placebo vs 36 allogenic myeloma) would provide 80% power to detect an increase in the median PFS from 18 months in the control arm to 42.8 months in the pooled vaccine arm ($HR = 0.4199$) based upon a log-rank test assuming a two-sided type I error rate of 10% and a loss to follow-up rate of 1% per year (5% overall). The accrual rate is expected to be 2.3 per month. Due to the small sample size, no interim efficacy analysis is planned at this time.

Our principal secondary endpoints will be conversion from “near CR” (M-spike at or below 0 but IFE positive), to “true CR” (IFE negative), and conversion from MRD positive status to MRD negative status. The trial will accrue patients for a total $n=18$ per arm at single center for a period two years, while trial duration for every patient enrolled will be 3 years. The analysis will be performed on the intention to treat population.

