11.2 Statistical Analyses

The efficacy and safety analysis populations will include all patients that received at least one dose of their assigned treatment. The primary analyses will compare the control arm with the pooled vaccine arm. Secondary analyses will compare the two vaccine arms to one another and to the control arm.

Demographic and disease characteristics will be summarized overall and within each treatment group using medians and ranges for continuous variables and counts and proportions for categorical variables.

The primary outcome (PFS) is defined as the time from randomization until progression or death. Individuals who do not have an event will be censored at the date of last assessment. Kaplan-Meier estimates of the survival function will be used to compare the two treatment groups graphically as well as to provide estimates of the median PFS and the proportion who have progressed at key time points (e.g. 1-, 2-, and 3-years) with 90% confidence intervals. Log-rank tests will be used to compare the treatment groups and Cox proportional hazards models will be used to examine the effects of specific risk factors of interest and their interaction with treatment (e.g. vaccine by MRD status interactions). If the proportional hazards assumption is violated, the piecewise proportional hazards models or other semi-nonparametric approaches will be used. Key secondary endpoints include conversion from “near CR” (M-spike at or below 0 but IFE positive), to “true CR” (IFE negative), and conversion from MRD positive status to MRD negative status. These and other time to event outcomes including will be analyzed in a similar manner to the primary outcome as well as with competing risk models to account for death or progression.

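### The protocol contradicts itself on whether progression is still assessed after a patient stops treatment for toxicity; read strictly, the operational text censors PFS early

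*Combined protocol and SAP*

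**What the plan says.** Three places give a rule for everyone.

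- Synopsis (Section 1): "All patients will be followed for a minimum of 3 years".
- Section 6.5, first sentence: "Patients will be followed for a minimum of 36 months after enrollment in the study or until relapse or death, whichever occurs first".
- Section 11.1: "Patients will be accrued over the course of 2 years with a minimum follow-up of 3 years". The same section names the intention-to-treat population and allows for loss of 1% per year, 5% in all.

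Four places govern what happens once treatment stops.

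- Section 6.5, second sentence: "Patients removed from study treatment for unacceptable adverse events will be followed until resolution or stabilization of the adverse event".
- Section 6.6, for grade 4 non-blistering rash and grade 4 neuropathy: "discontinue lenalidomide. Remove patient from study". Blistering rash of any grade carries the same instruction.
- Section 7.4: "Subjects who discontinue study treatment for any reason will undergo a safety assessment approximately 30 days post the last dose of study drug". No disease assessment is mentioned.
- Section 8 places efficacy measurement before the start of each lenalidomide cycle.

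The censoring rule in Section 11.2 is: "Individuals who do not have an event will be censored at the date of last assessment". Stopping treatment is not listed there as a reason to censor, nor is it ruled out.

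**The concern.** The primary outcome is time from randomisation to progression or death. The analysis needs a progression status for each patient whether or not treatment continues. The sections that site staff carry out day to day do not ask for it after a toxicity stop, and one tells them to take the patient off the study. A patient off lenalidomide starts no further cycles, so the trigger in Section 8 lapses. Section 6.2.1 requires the patient to be on lenalidomide on each vaccine day, so the vaccine visits lapse too.

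If assessments cease, the last-assessment rule in 11.2 produces censoring at or shortly after removal. Removal for toxicity may be related to arm and to prognosis, so this censoring cannot be assumed independent of outcome. It also draws on a thin allowance: 5% of 54 is 2.7 patients, so three early-censored removals would exceed it before any ordinary loss. Progression dates not collected at the time may not be recoverable at analysis.

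**Working it through.** **Inputs from Section 11.1.** 18 control and 36 pooled vaccine patients; median PFS 18 and 42.8 months; HR 0.4199; two-sided alpha 10%; 24 months of accrual and 36 months of minimum follow-up, so 36 to 60 months per patient; loss 1% per year. The rate of stopping for toxicity is not given anywhere, so it is an assumption below.

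**Step 1: reproduce the stated 80% power.** Assume exponential PFS and uniform accrual. Monthly hazards are ln 2/18 = 0.03851 (control), ln 2/42.8 = 0.01620 (vaccine) and −ln(0.99)/12 = 0.00084 (loss). With λ the event hazard, η the loss hazard and h = λ + η, the event probability is

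P = (λ/h) × [1 − (e^(−36h) − e^(−60h))/(24h)].

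- Control: P = 0.825, so 18 × 0.825 = 14.9 events.
- Vaccine: P = 0.528, so 36 × 0.528 = 19.0 events.
- Total: 33.9 events.
- SE of log HR = √(1/14.85 + 1/19.01) = 0.346; |ln 0.4199|/0.346 = 2.506; power = Φ(2.506 − 1.645) = 80.5%.

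A log-rank simulation (10,000 runs) gives 80.7%. Other approximations range from 76.9% (Schoenfeld) to 82.9% (Freedman). The plan's figure reproduces.

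**Step 2: add early censoring for toxicity.** A proportion q stopped by month m adds −ln(1 − q)/m to η.

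| Assumed toxicity stops | Total censoring per year | Events | Power |
|---|---|---|---|
| None | 1.0% | 33.9 | 80.5% |
| 5% by 36 months | 2.7% | 33.0 | 79.6% |
| 10% by 36 months | 4.4% | 32.0 | 78.6% |
| 25% by 36 months | 10.1% | 29.2 | 75.4% |
| 19.8% by 17.6 months (stress case) | 14.8% | 27.0 | 72.6% |

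The 25% is the unacceptable-toxicity rate expected in Section 11.3, which is not a discontinuation rate. The stress case is the discontinuation figure and median follow-up that Section 4.2 reports for lenalidomide with dexamethasone in relapsed disease. Both are probably high here, because patients have already completed at least 6 cycles of a lenalidomide regimen.

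**Step 3: bias in 2-year PFS, vaccine arm, illustrative.** Suppose a share p stops at 6 months and then progresses at the control rate. The estimate with censoring stays near 0.5^(24/42.8) = 67.8%. The true value is (1 − p) × 0.678 + p × 0.907 × 0.5, where 0.907 = 0.5^(6/42.8) and 0.5 is control survival over the remaining 18 months.

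- p = 5%: 66.7%, bias 1.1 points.
- p = 10%: 65.6%, bias 2.2 points.
- p = 20%: 63.3%, bias 4.5 points.

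For scale, the standard error of a 2-year proportion with 36 patients is √(0.678 × 0.322/36) = 7.8 points.

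**Step 4: error rate under no effect.** One simulation (10,000 runs) links stopping to progression through an assumed gamma frailty of variance 0.5, with 5% control and 25% vaccine stops by 36 months. The two-sided error is 10.6% with censoring at the stop and 10.9% with continued follow-up, against a nominal 10%. Rejections favouring vaccine are 7.0% and 6.2%.

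**The case against.** A reader might infer that follow-up ends when treatment ends, that PFS is censored at that moment, and that the 1% loss assumption is therefore broken. The documents do not support this.

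- Section 6.5 does not limit follow-up to the adverse event. Its second sentence concerns patients removed from study treatment and reads naturally as an added safety duty. The sentence before it, the synopsis and Section 11.1 set the 36-month minimum without exception.
- Section 11.2 censors at the last assessment. Even on the strict reading, contact runs to resolution or stabilisation of the event, or to the visit at about 30 days.
- The Section 2 schedule has calendar visits at 1 year, 18 months, 2 years, 30 months and 3 years, with electrophoresis, light chains, immunofixation and response assessment. The 18- and 30-month visits include no vaccine. The off-study label in these column headings does not confine them to patients on treatment.
- No toxicity-stop rate is given, and most toxicities in 6.6 lead to a hold or a dose reduction. Only three lead to removal from the study.
- Differential removal is weakly supported. Section 6.2.4 describes mostly grade 1-2 local reactions, whereas removal requires grade 4 or blistering rash, or grade 4 neuropathy.
- The bias example is one-sided. If 20% of control patients also stopped at 6 months with the same relative rise in hazard, the true 2-year difference would be 28.5 points against 28.1 with censoring.

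All of this stands against the stronger reading. It does not remove the conflict. For the three toxicities in 6.6 the instruction concerns the study, not the treatment, so reading 6.5 as an added duty does not rescue those patients. Nothing states affirmatively that the calendar visits continue off treatment.

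**Conclusion.** The contradiction is real and touches the primary endpoint. Whether patients who stop for toxicity stay under assessment for progression depends on which section is followed. On the strict operational reading they are censored at or soon after removal, for a reason that may relate to treatment and prognosis, and the 1% annual loss would be exceeded. On the other reading there is no loss.

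The numerical effect is modest: about 1 to 5 points of power for 5% to 25% stopped by 36 months, and about 1 to 4.5 points of bias in one arm's 2-year PFS for 5% to 20% stopped at 6 months. These figures rest on exponential PFS and assumed stop rates.

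The case for acting is therefore avoidable loss of primary-endpoint data and fidelity to intention to treat, rather than power. Continued follow-up restores 33.9 events and 80.5% power only if stopping leaves the hazard unchanged. If the hazard doubled after stopping, with 5% of control and 15% of vaccine patients stopping per year, simulated power would be 75.7% with censoring and 73.1% with follow-up. The second figure is the one that belongs to the randomised comparison.

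**What to change.** Reconcile Sections 6.5, 6.6, 7.4 and 8 with the synopsis and Section 11.1.

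- **6.5 and 6.6:** define removal from study treatment separately from withdrawal from the study, and say which is meant at each of the three toxicities. The clinical rules for stopping lenalidomide are not part of this point and do not change.
- **6.5, 7.4 and 8:** state that every randomised patient who stops treatment for a reason other than progression continues the scheduled myeloma laboratory assessments, on the same calendar, until progression, death, withdrawal of consent or data cut-off. Present follow-up of the adverse event and the 30-day visit as additions to this.
- **11.2:** state that stopping treatment is not a reason for censoring. A short sensitivity analysis for early censoring would cover patients who are lost anyway.

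The sample size stays at 54. The cost is an amendment to wording, plus the collection of routine myeloma laboratory results for what is likely to be a few patients off treatment.
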